| 
Study objectives
 | 
 ● To describe the characteristics of COVID-19 and its sequelae in several types of fragile populations. ● To describe the rate, the etiology (SARS-CoV-2 variants), the severity of COVID-19, and the rate of re-infections in several types of fragile patients. ● To evaluate the immunologic response to the COVID-19 vaccination in selected fragile populations. ● To evaluate the safety of COVID-19 vaccination in selected fragile populations. |

| | |
|--------------------|--|
| | 
 Identify human genetic markers and epigenetic characteristics in frail patients during post-vaccination monitoring and in case of breakthrough infections as well as to analyse the gut microbiome in such patients |
| Study population | Patients of all age and any comorbidity included in an ORCHESTRA fragile population cohort |
| Inclusion criteria | 
 Any age Any comorbidity Person (or attorney or deputy who has been authorized to make the decision for patients who lack capacity) consent to participate or appropriate local waiver of consent. |
| Exclusion criteria | Patients did not agree to participate. |
| Study design | 
Multicenter, multinational observational study aimed at building several types of fragile populations in which to assess the rate and the clinical spectrum of COVID-19, with particular interest in long-term follow-up, and at monitoring clinical and immunological response after SARS-CoV-2 vaccination in fragile subjects.
 
For long-term follow-up of fragile patients with COVID-19, a predefined schedule of assessment is planned in alignment with Work Package (WP) 2. Patients already diagnosed with COVID-19 can be included if baseline data according to WP2 protocol have been collected, and if follow-up visits are possible.
 
For assessing the clinical and immunological response to vaccination, patients will be prospectively evaluated at baseline (first and
 |

| | |
|--------------------|---|
| | second vaccination doses), and at multiple timepoints after vaccination with clinical and immunological assessments. |
| Vaccines | Approved COVID-19 vaccines |
| Follow-up | Patients will be followed-up for up to 18 months after the SARS-CoV-2 infection diagnosis or up to 12 months after vaccination. |

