11. Symptoms: abdominal pain, ageusia/dysgeusia, anosmia, balance impairment, behaviour disorder, chest pain or chest tightness, confusion, cough, delirium, diarrhoea, disrupted sleep, dizziness, dyspnoea, fatigue, fever (including low-grade fever), headache, hypothermia, impaired cognitive status, lethargy, loss of appetite, mood affective disorder, myalgia, nausea/vomiting, palpitation, phlegm, runny nose, sore throat, stuffed nose, syncope, wheeze.
12. WHO Clinical Progression Scale
13. Vital signs: dead/alive, blood pressure, body temperature, heart rate, respiratory rate, peripheral oxygen saturation
14. Physical examination: BMI, abdominal examination, pulmonary examination, cardiac examination, neurological examination, peripheral vascular examination
15. Pulmonary function test: FEV₁, FVC, FEV₁/FVC, TLC, FRC, RV
16. Questionnaires to address the functional status: Post-COVID-19 Functional Status (PCFS) Scale, Global Physical Activity, Questionnaire (GPAQ), Barthel Index, Medical Outcome Study Short Form (MOS SF)-36 Score, EuroQol five-dimension five-level (EQ-5D-5L) questionnaire, Clinical Frailty Scale (CFS), Basic Activity of Daily Living (BADL).
17. Questionnaires to address the respiratory impairment: Saint George Respiratory Questionnaire (SGRQ), Transition Dyspnoea Index (TDI), mMRC (Modified Medical Research Council) Dyspnea Scale
18. Questionnaires to address the mental health: Hospital Anxiety and Depression Scale (HADS), Kessler Psychological Distress Scale (K10), Impact of Event Scale – Revised (IES-R), Resilience Scale for Adults (RSA)
19. Perceived risk of re-infection on a scale 0-10 (no risk- very high risk); perceived risk of admission/re-admission on a scale 0-10 (no risk- very high risk)
20. Frequency mask-wearing (type of mask); frequency hand washing; respect of social distance; avoidance of social gathering

21. Was the vaccine accepted? Why not accepted (lack of trust in efficacy and/or safety; not useful in the specific case; prefer someone else gets it before me)
22. Cardiac MRI only if abnormal cardiac ultrasound
23. Blood tests: White blood cell count, lymphocyte count, neutrophil count, platelets, sodium, potassium, creatinine, glucose, bilirubin, alanine aminotransferase, aspartate aminotransferase, gamma glutamyl transpeptidase, albumin, lactate dehydrogenase, ferritin, creatine kinase, fibrinogen, INR, partial thromboplastin time, D-dimer, NT-pro-BNP, troponin, C-reactive protein (CRP), procalcitonin, venous lactate

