| Metagenomic sequencing | X | | X | | |
| Questionnaires¹ | | | | | |
| Risk perception and behavior | X ¹ | | | X | X |
| Socio-economic indicators | X ¹ | | | X | X |
| Use of resources (COVID-19 unrelated) | X ¹ | | | X | X |
| Adverse Events dedicated questionnaire | | X | X | X | X |
| Immune response | | | | | |
| Quantitative Ab anti-S IgG ⁵ | X | X | X | X | X |
| Qualitative Ab anti-N IgM+IgG ⁵ | X | | | | |
| Anti-SARS-CoV-2 sero-neutralization | X | X | X | X | X |
| Cytokine / chemokines | X | X | X | X | X |
| Anti-SARS-CoV-2 cell immunity | | X | | X ⁶ | X ⁶ |

Footnotes

Modular data capture according to level of commitment (level I, level II).

| | |
|----------|---|
| Level I | Assessments in level I are core and should be prioritized |
| Level II | Customized according to the feasibility of each cohort |

*3, 6 and 12 months counted from the 1st dose.

¹For centers able to follow patients since the administration of the first and second vaccination doses the baseline information and the risk perception behavior should be collected at one of these time-points, in the other cases such information should be collected during the first post-vaccination follow-up.

²The assessment at 2nd dose is mandatory in patients who will receive such dose within 8-12 weeks after first dose (current AstraZeneca vaccination schedule).

³If COVID-19 diagnosis, assessments reported in Table 1 are required.

⁴Relevant new medical events or worsening of previous conditions, including new malignancies (type of cancer, overall stage, Kaposi skin-visceral, Lymphoma localization-type, Leukemia lymphoid-myeloid acute-chronic), deep venous thrombosis, pulmonary embolism, infections (including a new SARS-CoV-2-infection during follow-up)

⁵At least one time-point at 1st and 2nd dose is required.

⁶At least one of the three timepoints (month 3, month 6, month 12) is required.

⁷At least one of the four timepoints (2nd dose, month 3, month 6, month 12) is required.

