7. OBJECTIVES

The primary objective of the ORCHESTRA fragile cohorts is to provide an extensive and harmonized collection of epidemiological and clinical data, and biological samples, to assess several features of COVID-19 in each cohort of fragile patients. These include:

- To assess the prevalence of SARS-CoV2 infection and COVID-19 disease in fragile patients;
- To describe the clinical spectrum of COVID-19 disease in different types of fragile patients;
- To analyze epidemiological, clinical and biological predictors of SARS-CoV-2 infection and prognosis in several types of fragile patients;
- To investigate the therapeutic management of COVID-19 and /or of the underlying condition and its impact on the outcome in fragile patients;

- To describe safety and efficacy of COVID-19 vaccination in selected cohorts of fragile patients;
- To describe the relationship between risk perception and adherence to preventive measures over time, including vaccine acceptance;
- To analyze the impact of COVID-19 pandemic on the use of health care services;
- To analyze the socio-economic determinants of infection and disease severity, and the socio-economic impact of the pandemic on cohort specific socio-economic indicators;
- To investigate the psychological consequences of lockdown in fragile patients.
- Identify human genetic markers and epigenetic characteristics in frail patients during post-vaccination monitoring and in the onset of breakthrough infections as well as to analyse the gut microbiome in such patients

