For patients with a past and/or new diagnosis of SARS-CoV2 infection/COVID-19 disease a pre-established long-term follow-up including multiple diagnostic levels in order to adapt to all the participating cohorts is requested. A detailed overview of the schedule of the study visits and the clinical parameters to be recorded is shown in **Table 1**. Patients who have already had COVID, and new patients being diagnosed with COVID, who can be followed up to at least 12 months, and for whom data can be collected according to **Table 1** should be included. In specific fragile cohorts, such as children cohorts, virtual assessments are allowed.

For patients who have been or will be vaccinated against COVID-19 during the study period, a pre-established monitoring of safety and efficacy in terms of immunological response will be performed. A detailed overview of the schedule of the clinical and laboratory parameters to be recorded is shown in **Table 2**. Patients who have already been vaccinated, or will be vaccinated, who can be followed for 12 months, and for whom data can be collected according to Table 2 should be included. The monitoring should start from the days of first and second dose administration when possible (i.e. vaccination administered in the same center where the patient is followed for the fragile condition), alternatively patients will be monitored at 3±1, 6±2 and 12±3 months after the first vaccination dose.

- Vaccination safety will be assessed by a dedicated questionnaire (Annex 3) distributed to patients at baseline or during the first monitoring visit.

- Vaccination efficacy will be established analyzing the immune response at the predefined time-points. The humoral immune response to vaccination will be assessed by a serological assay able to detect anti-Spike and anti-Nucleocapsid antibodies as well as seroneutralization assays in sera samples. The latter will be useful to exclude possible natural infection at the baseline (1st/2nd dose, or first post-vaccination monitoring visit). The cytokine and cell-mediated immune response to vaccination will be assessed in a subgroup of patients by centralizing samples to a referral laboratory, according to local ethic rules and budget. The number of SARS-CoV-2 paucisymptomatic or symptomatic infection despite vaccination will be also assessed by SARS-CoV-2 detection in respiratory/saliva sample.

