ANNEX 3 – Questionnaire for monitoring of adverse events to COVID-19 vaccination

A) Demographics – Anamnesis

Age: _____

Sex: M F

Special population: HIV Cancer Solid organ transplant Haematological stem cell transplant

If solid organ transplant, please specify: Liver Kidney Heart Lung

Drug/food allergies: Y N If yes, please specify: _____

Previous serious adverse events to vaccination: Y N

Underlying diseases:

Renal Cardiovascular Asthma Diabetes mellitus Anaemia/Blood disorders

Seizure/Epilepsy

Other nervous system disease: Y N If yes, please specify: _____

Concomitant medications: _____

Blood transfusion in the last year: Y N

Treatment with immunoglobulin or antivirals in the last year: Y N

Other relevant conditions: _____

B) Adverse event report

First dose (dd/mm/yy): _____

Second dose (dd/mm/yy): _____

Clinical events after the first dose: Y N

Clinical events after the first dose: Y N

Headache: Y N

Asthenia: Y N

Fever ($\geq 38^{\circ}\text{C}$): Y N

Nausea: Y N

Vomiting: Y N

Lymphadenopathy: Y N

Tachycardia: Y N

Flushing: Y N

Syncope: Y N

Pruritus, erythema or pain in injection site: Y N

- Generalised urticaria: Y N
- Serious allergic events (anaphylaxis, angioedema): Y N
- COVID infection after vaccination: Y N
- Use of paracetamol or non-steroidal anti-inflammatory drugs: Y N
- Requirement for use of other drugs: Y N If Yes, please specify: _____
- Demyelinating disorders: Y N
- Encephalitis/Encephalopathy: Y N
- Peripheral neuropathy: Y N
- Muscular weakness and/or paralysis: Y N
- Visual impairment (including optic neuritis): Y N
- Walking disturbance: Y N
- Blood disorders (anaemia, thrombocytopenia, leukopenia): Y N
- Seizures/Epilepsy: Y N
- Weakness and/or paralysis of facial muscle: Y N
- Vasculitis: Y N
- Renal disorders: Y N
- Liver function disorders: Y N
- Cardiac disorders: Y N
- Other adverse events: Y N If Yes, please specify: _____

[figure not shown]
If yes (complete for each reported event): day of onset (dd/mm/yy): _____

hospitalization/emergency department admission/general practitioner visit: Y N

Description of the event (laboratory data/administered drugs/other relevant information):

Recovery: Y N

ANNEX 4 – WP6 Deliverable 6.1_Mapping of retrospective samples and development of standardized protocols for prospective sampling

WP6 Deliverable 6.1

Mapping of retrospective samples and development of
standardised protocols for prospective sampling

UANTWERPEN

Project Classification

| | |

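### Annex 3's coded fields cannot separate a hospital admission from a GP visit, or a death from non-recovery, after vaccination

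*Protocol*

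**What the plan says.** Vaccine safety is a stated aim. The synopsis lists "To evaluate the safety of COVID-19 vaccination in selected fragile populations", and section 7 repeats it as "To describe safety and efficacy of COVID-19 vaccination in selected cohorts of fragile patients".

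Section 11 names the instrument: "Vaccination safety will be assessed by a dedicated questionnaire (Annex 3) distributed to patients at baseline or during the first monitoring visit". Table 2 schedules an adverse-event questionnaire at the second dose and at 3, 6 and 12 months.

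Part B of Annex 3 has a list of yes/no items by type of event, among them "Serious allergic events (anaphylaxis, angioedema): Y N" and several neurological, cardiac, renal and blood disorders. For each event reported, it then asks for four things:

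- the day of onset;
- "hospitalization/emergency department admission/general practitioner visit: Y N";
- free text, "Description of the event (laboratory data/administered drugs/other relevant information";
- recovery, yes or no.

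Table 1, the schedule for COVID-19 follow-up, has a vital-signs row at every visit, which its footnote 13 defines as "Vital signs: dead/alive, blood pressure" and further measurements. Table 2, the post-vaccination schedule, has no vital-signs or vital-status row.

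**The concern.** Admission to hospital and death are what a reader of a vaccine safety report in fragile patients will look for first. Section 6 itself raises vaccine adverse reactions in these populations, citing a report (reference 11) on deaths in frail elderly patients after vaccination. The instrument named for this purpose puts three very different levels of care into one answer and offers no fatal outcome.

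This is a matter of data capture and cannot be left to a later analysis plan. Once the answers are collected as a single tick, no analysis of the coded data can split them. The study would then report a rate of any medical contact after vaccination, and could not say from the coded fields how many of those contacts were admissions.

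**Working it through.** No figure in the protocol depends on this item, so there is nothing to reproduce. The check compares what the form codes with what the rest of the protocol collects on vaccinated patients.

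| Needed for the safety objective | Annex 3 coded fields | Elsewhere in the protocol |
|---|---|---|
| Event led to admission | Not separable: one yes/no for three levels of care | Table 2 row for relevant new medical events (footnote 4), with no admission field specified |
| Event was fatal | Not separable: the only alternative to recovered is not recovered | All-cause mortality in section 12, not linked to a reported event |
| Severity grade | None | CTCAE appears only in the Table 1 footnotes, where it fits the onco-haematology adverse-event row |
| Vital status at the visit | None | Table 1 only; Table 2 has no such row |
| Event of a serious type | Coded by type, for example serious allergic events, encephalitis, seizures | Table 2, footnote 4: thrombosis, embolism, infection, malignancy |

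Three things follow.

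1. **Admission.** A yes on the combined item means at least one of three contacts. The coded data hold nothing further on which one it was. The free text may say, but it is not a standard field that can be counted across the 29 cohorts in 14 countries described in section 9.
2. **Fatal outcome.** A no on recovery means either still unresolved or died. The date of death, if collected for the mortality endpoint, can be set against the dose dates on the form. That gives deaths after vaccination, but not deaths as the outcome of a reported event.
3. **Vital status.** Under footnote 3 of Table 2, a vaccinated patient who develops COVID-19 moves to the Table 1 assessments, which include dead/alive. The gap therefore concerns vaccinated patients without COVID-19, for whom the schedule has no place to record vital status at a visit.

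**Illustration, on assumed counts only.** Suppose 1,000 vaccinated patients, one event each at most and no overlap between contacts: 50 with a GP visit, 10 with an emergency visit and 5 admitted.

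- Combined tick: 50 + 10 + 5 = 65, and 65/1,000 = 6.5%.
- Admissions: 5/1,000 = 0.5%.
- Range compatible with the coded field alone: 0/1,000 to 65/1,000, that is 0 to 6.5%.

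The counts are invented to show the loss of information. They do not estimate what this study would see, and the free text could narrow the range.

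**The case against.** The strongest reply is that Annex 3 is not the only source, and much of this stands.

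- **Deaths.** All-cause mortality during follow-up is an endpoint in section 12 and is not restricted to COVID-19 patients. Section 13 plans Cox models for each endpoint, including death. Section 14.4 provides for retrospective data collection after a patient's death, and section 14.5 draws on the medical file. A reader might infer from the form that fatal events cannot be counted or drop out of the study. The documents do not support that.
- **Serious events.** Many can be counted by type, from Annex 3's own condition items and from the Table 2 row for new medical events, which is scheduled at both doses and at 3, 6 and 12 months.
- **Who completes the form.** Section 11 says it is distributed to patients, but not who fills it in. Its request for laboratory data suggests possible staff input, and section 14.6 makes the investigator responsible for verifying entries. It cannot be concluded that a patient who dies has no form. With four scheduled questionnaires, a patient who dies later may already have reported.
- **Direction of bias.** A reader might infer that the safety conclusion is tilted towards reassurance. The documents do not show this. If the combined tick were read as admissions, it would overstate them.
- **Descriptive aim.** The study is observational, its safety aim is descriptive and the vaccines are approved, so formal severity grading is partly a matter of preference.

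None of this reaches the central point. The other sources give deaths from any cause and events by type. They do not give, in a coded and uniform way, whether a reported adverse event led to admission or to death. Section 14.4 is also not tied to Annex 3, so nothing says that the form is completed for a patient who has died.

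**Conclusion.** The point holds in a limited form. From the per-event coded fields of the protocol's named safety instrument, admission cannot be distinguished from an emergency or GP visit, and death cannot be distinguished from non-recovery. Table 2 adds no vital-status item to fill the second gap. As a result, a standard rate of adverse events leading to admission or death after vaccination cannot be derived, although deaths overall and some serious events by type can still be counted.

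The size is not known from the documents; the 6.5% against 0.5% above is an assumption. The conclusion rests on the form's text, which shows one yes/no for the three levels of care. If the sponsor's form has separate boxes for each, the first half falls and the second half remains. The change is worth making because it bears directly on a stated objective and cannot be repaired after collection.

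**What to change.** 1. In Annex 3, part B, replace the combined item with three separate yes/no items: GP visit, emergency department visit, hospital admission.
2. Replace the yes/no on recovery with four categories: recovered, not recovered, sequelae, died.
3. Add the dead/alive item from Table 1 to the follow-up visits in Table 2.
4. State in section 11 that the site completes Annex 3 from the medical record when a patient has died, in line with the retrospective collection already provided for in section 14.4.
5. State that adverse events leading to admission or death will be reported separately from the others.

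The cost is a few extra fields on an existing form, one row in the eCRF, and a little site time for patients who have died. Patient care and the visit schedule are unaffected. Where forms have already been completed, sites could recover the split from the free text or the medical record, which takes more effort than collecting it at the time.

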1. INTRODUCTION TO ORCHESTRA

ORCHESTRA is a three-year international research project aimed at tackling the coronavirus pandemic, led by the University of Verona and involving 26 partners (extending to a wider network of 37 partners) from 15 countries: Argentina, Belgium, Brazil, Congo, France, Gabon, Germany, India, Italy, Luxemburg, Netherlands, Romania, Slovakia, Spain, Venezuela. The project is divided into a retrospective and a prospective tier in which clinical data and biosamples are analysed in order to

- develop evidence-based recommendations for effective prevention, protection and optimized treatment of COVID-19 patients (including long-term sequelae) with a special focus on ‘at risk’ populations, including healthcare workers and fragile individuals
- assess impact of environmental factors, socio-economic determinants, lifestyle and confinement measures on the spread of COVID-19
- provide knowledge on the efficacy of vaccines against SARS-CoV-2
- provide a model for responsiveness for future pandemic outbreaks.

2. OBJECTIVES AND BRIEF DESCRIPTION OF SUBSTUDIES WITHIN WP6

Several different sample types will be analysed within the ORCHESTRA study for the purposes of identifying human and viral genetic markers indicative of disease severity as well as to study immune responses over time as a result of infection and immunization. Specifically, samples will be collected from patients developing COVID-19 (including breakthrough and reinfection) in order to study both short- and long-term effects of infection on host immunity, respiratory and intestinal microbiome dynamics as well as host and viral genetic determinants underlying infection. Additionally, samples will be collected from vaccinated fragile populations as well as vaccinated healthcare workers in order to study effects of vaccination on host immunity and respiratory and intestinal microbiome dynamics.

Samples collected within the framework of the ORCHESTRA study will in many cases be subjected to more than one type of analysis. To provide an overview of research questions of interest within the project, a brief summary of each analysis can be found below.

2.1 CHARACTERISATION OF SARS-COV-2 VIRAL VARIANTS (TASK 6.2)

This task will target two main points among selected patient populations: [i] to characterise the viral variants and to identify variants of concern (VOCs) by whole genome sequencing (WGS) in COVID-19 patients and in vaccinated individuals with breakthrough infections, and [ii] to study potential

mutation selection in populations presenting with long viral replication or receiving immunoglobulin therapies, and [iii] to study the viral replication (viral load and excretion duration).

